8.1.6. Summaries of Adverse Events and Deaths

A brief, high-level summary of the number and percentage of subjects who experienced at least 1 TEAE in the categories described below will be provided by treatment for the double-blind phase, open-label filgotinib phase, and for an “as-treated” display:

- TEAE
- TEAEs with Grade 3 or higher (further broken down to Grade 3, Grade 4, and Grade 5)
- TEAEs with Grade 2 or higher
- TE treatment-related AE
- TE treatment-related AEs with Grade 3 or higher (further broken down to Grade 3, Grade 4, and Grade 5)
- TE treatment-related AEs with Grade 2 or higher
- TE SAE
- TE treatment-related SAE

- TEAE that led to premature discontinuation of double-blind study drug (displayed for double-blind phase analysis only)
- TEAE that led to premature discontinuation of open-label filgotinib study drug (displayed for open-label phase analysis only)
- TEAE that led to temporary interruption of double-blind study drug (displayed for double-blind phase analysis only)
- TEAE that led to temporary interruption of open-label study drug (displayed for open-label phase analysis only)
- TEAE that led to premature discontinuation of study
- All deaths observed in the study (if subject received ≥ 1 dose of open label filgotinib will be summarized with open-label filgotinib; if last study drug received was double-blind, will be summarized with double blind study drug)

The number and percentage of subjects who experienced at least 1 TEAE will be provided and summarized by SOC, HLT, PT, and treatment for the double-blind phase and for an “as-treated” analysis.

The following 2 tables will be displayed for the double-blind phase of the study for subjects in the Safety Analysis Set:

- The number and percentage of subjects who experienced TEAEs leading to temporary interruption of double-blind study drug
- AEs leading to premature discontinuation of double-blind study drug

Similar tables will be displayed for the open-label filgotinib phase of the study for subjects in the Open-Label Filgotinib Safety Analysis Set:

- The number and percentage of subjects who experienced TEAEs leading to temporary interruption of open-label filgotinib
- AEs leading to premature discontinuation of open-label filgotinib

For other AEs described below, summaries (for the double-blind phase and for “as-treated” analysis) will be provided by SOC, PT, and treatment:

- All TEAEs
- All TEAEs by Concomitant Medication Use (Immunomodulator and Corticosteroid Use)
- TEAEs of Grade 3 or higher (by maximum severity)

- TEAEs of Grade 2 or higher
- TE treatment-related AEs
- TE Treatment-related AEs of Grade 3 or higher (by maximum severity)
- TE SAEs
- TE SAEs by Concomitant Medication Use (Immunomodulator and Corticosteroid Use)
- TE treatment-related SAEs
- TEAEs leading to premature discontinuation of study
- TEAEs leading to death

Multiple events will be counted only once per subject in each summary. Adverse events will be summarized and listed first in alphabetic order of SOC and HLT within each SOC (if applicable), and then by PT in descending order of total frequency within each SOC. For summaries by severity grade, the most severe grade will be used for those AEs that occurred more than once in an individual subject during the study.

In addition to the above summary tables, all TEAEs, SAEs, and TE treatment-related AEs will be summarized (for the double-blind phase and for “as-treated” analysis) by PT only, in descending order of total frequency.

In addition, data listings will be provided for the following:

- All AEs, indicating whether the event is treatment emergent
- All AEs of Grade 3 or higher
- SAEs
- Deaths
- COVID-19 Adverse Events
- All AEs leading to temporary interruption of double-blind study drug
- All AEs leading to temporary interruption of open-label filgotinib study drug
- AEs leading to premature discontinuation of double-blind study drug
- AEs leading to premature discontinuation of open-label filgotinib study drug

8.1.7. Adverse Events of Interest

Adverse events of interest (AEIs) include infections, gastrointestinal perforations, herpes zoster, malignancies (excluding non-melanoma skin cancers), non-melanoma skin cancers, and thromboembolic events. Summaries of the following treatment-emergent AEIs will be produced to enhance the analysis of safety data.

- Events of infection presented in the following subcategories:
 - AEs of infections, utilizing all AEs in the MedDRA Infections and Infestations SOC
 - AEs of serious infections, using all AEs in the MedDRA Infections and Infestations SOC that are classified as SAEs
 - AEs of herpes zoster, utilizing a MedDRA search term (MST) list developed by Gilead
 - AEs of opportunistic infections (OIs), using a Standardized MedDRA Query (SMQ)--narrow scope
 - Active tuberculosis, using an MST list developed by Gilead
 - Hepatitis B or C infections, using an MST list developed by Gilead
- AEs of malignancies, excluding non-melanoma skin cancers, utilizing a MST list developed by Gilead
- AEs of non-melanoma skin cancers, utilizing a MST list developed by Gilead
- AEs of gastrointestinal perforation, utilizing a MST list developed by Gilead
- AEs of arterial or venous thrombosis and/or thromboembolism, presented in the following subcategories:
 - AEs of venous thrombosis, utilizing a MST list developed by Gilead
 - AEs of pulmonary embolism, utilizing a MST list developed by Gilead
 - AEs of arterial thrombosis, utilizing the embolic and thrombotic events, arterial Standardised MedDRA Queries (SMQ)
 - AEs of cerebrovascular events, utilizing the ischaemic central nervous system vascular conditions SMQ

For the double-blind phase, the number of subjects with a TE AEI (and SAE), the corresponding PYE, the calculated EAIR, and the exact 95% CIs (defined in Section 8.1.5.3) will be summarized for each treatment group by PT. The EAIR difference (filgotinib – placebo) and corresponding 95% CIs for the difference between treatment groups will also be presented for the double-blind phase of the study.

For the overall study, the number of subjects with a TE AEI in each category (and separately for SAEs), the corresponding PYE, the calculated EAIR, and the exact 95% CIs (defined in Section 8.1.5.3) will be summarized for each treatment group (filgotinib and placebo) by PT using an as-treated analysis. Filgotinib group includes the filgotinib exposure for the placebo to filgotinib sequence, and exposure for DB filgotinib and filgotinib to OL filgotinib treatment sequences. Placebo will include DB Placebo and the placebo exposure for the Placebo to OL filgotinib treatment sequence.

Data listings for each AEI will also be provided.

8.1.7.1. Cardiovascular Event Adjudication Committee

An independent cardiovascular event adjudication committee (CVEAC) reviews and adjudicates all potential MACE and thromboembolic events in a blinded manner. To identify potential MACE and thromboembolic events, the following AEs will be sent for adjudication. Please refer to the Cardiovascular Event Adjudication Committee Charter for more details.

- All AEs leading to death
- CV events (meeting serious criteria), utilizing a MST list developed by Gilead
- MI, utilizing a narrow scope Standardized MedDRA Query (SMQ)
- Unstable angina (meeting hospitalization criteria), utilizing a MST list developed by Gilead
- Transient ischemic attack, utilizing a MST list developed by Gilead
- Stroke, utilizing a MST list developed by Gilead
- Cardiac failure (meeting hospitalization criteria), utilizing a MST list developed by Gilead
- Percutaneous coronary intervention, utilizing a MST list developed by Gilead
- Embolic and thrombotic events, utilizing a narrow scope SMQ

The CVEAC will review the above AEs, and related clinical data to adjudicate whether the criteria for MACE (CV death, MI, and/or stroke), ASTE, and VTE have been met for each AE.

The number and percentage of subjects with positively adjudicated TE MACE, TE ASTE, and TE VTE will be summarized by treatment group using the adjudicated category if applicable for the final analysis of the study only.

A by-subject listing for subjects with potential events for adjudication (MACE, ASTE, and VTE) and their respective adjudication results will be provided for interim and final analyses of the study.

A by-subject listing of thromboembolic history and risk factors will be provided for subjects with potential events for adjudication (MACE, ASTE, and VTE), if applicable.

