3.1.3. Safety Analysis Sets

The Safety Analysis Set includes all randomized subjects who took ≥ 1 dose of double-blind study drug. This is the analysis set utilized for safety analyses during the double-blind phase of the study.

The Open-Label Safety Analysis Set includes all randomized subjects who took ≥ 1 dose of open-label filgotinib study drug in the Open-Label Phase of the study. This analysis set will be used for selected safety displays during open-label filgotinib treatment (eg, brief summary of AEs, interruption of open-label filgotinib, discontinuation of open-label filgotinib).

The As-Treated Safety Analysis Set includes all subjects in the Safety Analysis Set; subjects initially randomized to placebo who switched to open-label filgotinib will also be included for the filgotinib group. This analysis set will be utilized to summarize all available on-treatment safety data during the study.

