- Subjects with a decrease of $\geq 50\%$ in sperm concentration and/or motility and/or morphology from baseline will have study drug stopped and an investigator selected standard of care treatment that is in accordance with the protocol started. Semen samples will be collected off study drug treatment every 13 weeks during the Monitoring Phase until reversibility is met or for up to 52 weeks, whichever occurs first. Reversibility is met when all sperm parameter(s) qualifying the subject to enter the Monitoring Phase return to greater than 50% of the baseline value (ie, greater than $0.5 \times$ [mean of 2 evaluable samples collected at the screening visit]). Data will be summarized for each sperm parameter meeting a pre-specified sperm decrease threshold at the visit when study drug was stopped. The number (percent) who met reversibility criteria and the cumulative number (percent) who met reversibility criteria at each Monitoring Phase visit will be presented separately for subjects who met pre-specified sperm decreases at Week 13 (summarized by double-blind treatment group) and for subjects meeting pre-specified sperm parameter decrease thresholds at the Week 26/OL Week 13 analysis visit or at/after Week 39/OL Week 26 and up to last dose date of any study drug + 7 days (summarized by treatment sequence).

The following subject groupings will be applied to safety data according to the actual treatment received (filgotinib or placebo) unless otherwise stated:

- An “as-treated” analysis will be performed for safety data. Subjects who took double-blind placebo and switched to open-label filgotinib will have data reported during the placebo period summarized with the placebo group, and data reported during the open-label filgotinib period summarized with the filgotinib group (baseline will be open-label baseline). Subjects who switch from double-blind filgotinib to open-label filgotinib and subjects who stay on double-blind study drug for the duration of study will be summarized by their double-blind treatment group (baseline will be double-blind baseline).

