8.1.5.3. Analysis of Exposure-Adjusted Incidence Rates

The Exposure-Adjusted Incidence Rate (EAIR) is defined as:

$$\begin{aligned} & \text{Incidence rate per 100 patient years of exposure (PYE)} \\ & = \frac{\text{Total number of subjects with an event}}{\text{Total PYE}} \times 100. \end{aligned}$$

The total patient-years of exposure (PYE) to a treatment is the sum of the individual subject's PYE, which is defined as:

- For subjects with an event:

$$PYE = (Event\ start\ date - first\ dosing\ date + 1) / 365.25.$$

When calculating PYE, a partial AE onset date will be imputed as follows:

- If the non-missing portion of the AE onset date (month and/or year) is the same as the portion of the first dosing date (month and/or year) of start of study drug, the AE onset date will be imputed as the first dosing date of study drug; otherwise it will be imputed as the 1st day of month (if only day is missing) or January 1st of the year (if day and month are missing).
 - If the AE onset date is completely missing, the AE onset date will be imputed as the first dosing date of study drug.
- For subjects with no event:

$$PYE = (Calculation\ end\ date - first\ dosing\ date + 1) / 365.25,$$

For double-blind phase:

First dosing date = double-blind first dose date

Calculation end date = earliest non-missing date of (last dosing date of double-blind drug + 30, first dosing date of OL filgotinib (if applicable) – 1, data cutoff date, death date)

For as-treated analysis:

Filgotinib exposure for Placebo to OL filgotinib: first dosing date = first dose date OL filgotinib; calculation end date is earliest non-missing date among (last dose date of OL filgotinib + 30 days, data cutoff date, death date)

Placebo exposure for Placebo to OL filgotinib: first dosing date = first dose date placebo; calculation end day is earliest non-missing date among (first dose date OL filgotinib – 1, data cutoff date, death date).

Exposure for subjects remaining on double-blind drug: first dosing date = first dose date double-blind drug; calculation end date is earliest date among (last dose date double-blind drug + 30, data cutoff date, death date)

Filgotinib exposure for Filgotinib to OL filgotinib: first dosing date = first dose date double-blind drug; calculation end day is earliest non-missing date among (last dose date of open-label filgotinib + 30, data cutoff date, death date).

The exact 95% CI based on Poisson distribution {Ulm 1990} for EAIR is defined as:

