$$\left(\frac{\chi^2_{2(\text{Total number of subjects with an event}),0.025}}{2 \times \text{Total PYE}}, \frac{\chi^2_{2(1+\text{Total number of subjects with an event}),0.975}}{2 \times \text{Total PYE}} \right) \times 100.$$

Partial last dosing dates of double-blind phase will be imputed as described in section 4.2.1.

In addition to by treatment group summary, the EAIR difference with 95% CI for filgotinib minus placebo will be presented. The Method of Variance Estimates Recovery (MOVER)-type confidence interval described in {Li 2011} will be used to calculate EAIR difference and 95% CI:

$$L = \frac{n_a}{T_a} - \frac{n_b}{T_b} - \sqrt{\left(\frac{n_a}{T_a} - l_a\right)^2 + \left(u_b - \frac{n_b}{T_b}\right)^2}, \quad U = \frac{n_a}{T_a} - \frac{n_b}{T_b} + \sqrt{\left(u_a - \frac{n_a}{T_a}\right)^2 + \left(\frac{n_b}{T_b} - l_b\right)^2},$$

where n_a is the total number of subjects with the event, T_a is the total PYE, l_a is the lower bound and u_a is the upper bound of the exact 95% CI based on Poisson distribution for group a .

Similarly for group b .

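### Adjudicated MACE, ASTE and VTE are reported only as n (%), although exposure per subject can differ between columns and the SAP already uses exposure-adjusted rates for search-term events

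*SAP*

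**What the plan says.** **Adjudicated events.** SAP 8.1.7.1 plans the number and percentage of subjects with positively adjudicated treatment-emergent MACE, ASTE and VTE. These "will be summarized by treatment group using the adjudicated category if applicable for the final analysis of the study only". By-subject listings of adjudication results accompany the interim and final analyses. No PYE, EAIR or confidence interval is mentioned.

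**Search-term events.** SAP 8.1.7 treats the adverse events of interest differently. For the double-blind phase it gives PYE, EAIR and exact 95% CIs, and the EAIR difference with "corresponding 95% CIs for the difference between treatment groups will also be presented for the double-blind phase of the study". For the overall study the same quantities "will be summarized for each treatment group (filgotinib and placebo) by PT using an as-treated analysis". The list includes venous, pulmonary and arterial thrombosis and "AEs of cerebrovascular events, utilizing the ischaemic central nervous system vascular conditions SMQ". It has no MACE category and no adjudicated category.

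**Columns.** SAP 3.2 introduces the as-treated rule with "The following subject groupings will be applied to safety data according to the actual treatment received (filgotinib or placebo) unless otherwise stated". In the As-Treated Safety Analysis Set (SAP 3.1.3), "subjects initially randomized to placebo who switched to open-label filgotinib will also be included for the filgotinib group". SAP 8.1.5.3 already defines the matching person-time, for example "Filgotinib exposure for Placebo to OL filgotinib: first dosing date = first dose date OL filgotinib", and states that "the EAIR difference with 95% CI for filgotinib minus placebo will be presented".

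**Pathways.** Under Protocol Section 3, Week 13 non-responders below the sperm-decrease thresholds leave blinded drug for open-label filgotinib. Under Protocol 6.10, responders at Week 26 or open-label Week 13 may stay on their current drug, blinded or open-label, in an extension of up to 195 weeks.

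**The concern.** A percentage compares risks fairly only when the columns have similar follow-up per subject, and this design does not ensure that. A Week 13 placebo switcher gives about 13 weeks to the placebo column and up to 13 + 195 = 208 weeks to the filgotinib column. A subject who stays on blinded drug can give up to 26 + 195 = 221 weeks to one column. Switchers also enlarge the filgotinib denominator.

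The adjudicated table appears only at the final analysis, when extension exposure is largest. With equal true rates, filgotinib looks worse if many open-label subjects continue into the extension and better if few do. The outcomes confirmed by an independent blinded committee would thus be shown with a weaker measure than the unadjudicated search-term events, and the SAP gives no reason for the difference.

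**Working it through.** **Plan's own figure.** 100 evaluable per arm with 20% non-evaluable: 100 / (1 − 0.20) = 125 per arm, 250 in total (Protocol 8.7, SAP 1.3). This reproduces. It is a ceiling here, because about 250 subjects are planned for this study and the rheumatic-disease study combined. The plan states no figure for adjudicated events.

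**Inputs.** From the documents: 13-week phases, an extension of up to 195 weeks, and as-treated exposure running to 30 days after last dose (SAP 8.1.5.3). The response pair 59%/41% is the Phase 2 Crohn's result in Protocol 1.3.2; SAP 6.7 notes that few Crohn's subjects were enrolled here. Other response rates, and extension entry, continuation and retention, are assumptions. Exits to the Monitoring Phase are not modelled.

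**(a) To Week 26 / open-label Week 13; no extension, dropout or 30-day tail.** With response r_p on placebo, in weeks per subject:

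- Placebo column = 13 + 13·r_p
- Filgotinib column = [26 + 13·(1 − r_p)] / (2 − r_p). Filgotinib non-responders stay in this column when they go open-label.

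| Response | Placebo | Filgotinib | Ratio |
|---|---|---|---|
| 50% both | 19.5 | 32.5 / 1.5 = 21.67 | 1.11 |
| 70% both | 22.1 | 29.9 / 1.3 = 23.0 | 1.04 |
| 30% both | 16.9 | 35.1 / 1.7 = 20.65 | 1.22 |
| 59% / 41% | 18.33 | 33.67 / 1.59 = 21.18 | 1.16 |

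**(b) With the extension, in years.** Let s be the share of double-blind responders who enter, c_f and c_p the shares of filgotinib and placebo switchers who continue, and L the mean extension time under exponential retention capped at 195 weeks. At 78% annual retention L = 2.43. Thirteen weeks is 0.249 y and 30 days is 0.082 y.

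- Placebo = 0.249 + r_p(0.249 + sL + 0.082)
- Filgotinib = [0.249 + r_f(0.249 + sL + 0.082) + (1 − r_f)(0.249 + c_f·L + 0.082) + (1 − r_p)(0.249 + c_p·L + 0.082)] / (2 − r_p)

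With s = 0.8 and 50/50 response:

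- Placebo = 0.249 + 0.5 × 2.28 = 1.39 PY per subject
- Filgotinib, c_f = c_p = 0: 1.72 / 1.5 = 1.15, ratio 0.83
- Filgotinib, c_f = 0.3 and c_p = 0.5: 2.69 / 1.5 = 1.80, ratio 1.29

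With 59/41 the two ratios are 1.02 and 1.56. With 50/50 and equal continuation, the ratio reaches 1 when about 15% of open-label subjects continue. Over s 0.4–1.0, c_f 0–0.5, c_p 0–0.6 and retention 60–90%, it runs 0.78–1.98 (50/50) and 0.99–2.28 (59/41). A separate model with fixed extension lengths of 0, 104 or 195 weeks and other response rates gave 0.76–1.92.

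**(c) Double-blind columns only.** The ratio is 1.00 with equal response. With 59/41 and the extension it is 1.27–1.37, because non-responders leave blinded drug at Week 13.

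**Effect on the table.** At an assumed true rate of 1 per 100 PY in both columns, case (b) 50/50 gives crude percentages (filgotinib vs placebo) of about 1.1% vs 1.4%, or 1.8% vs 1.4%. The EAIR is 1.0 in every column. Expected events at 100–125 per arm are 1.7–3.4 on filgotinib and 1.4–1.7 on placebo.

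**What the better display would show.** Take 125 per arm, response 59/41, open-label response 59% (placebo switchers) and 30% (filgotinib switchers), 104 extension weeks for each entrant and no other dropout. Then placebo has 150.3 PY in 125 subjects and filgotinib 361.4 PY in 125 + 0.59 × 125 ≈ 199. One placebo and three filgotinib events read 0.8% vs 1.5% as crude percentages. As rates per 100 PY they read 1 / 150.3 = 0.67 (0.02–3.71) vs 3 / 361.4 = 0.83 (0.17–2.43).

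**The case against.** **The display may not be as-treated.** SAP Section 8 opens by placing safety analyses on the Safety Analysis Set, which SAP 3.1.3 ties to the double-blind phase. Section 8.1.7.1 does not say as-treated, whereas 8.1.7 and 8.1.8 do. If the table is double-blind, switchers do not enter the filgotinib column. That stands as a reason to label the display. It does not remove the point: SAP 3.2 makes as-treated the default for safety data, SAP 8.2 itself applies an as-treated analysis to the Safety Analysis Set, and double-blind exposure is also unequal when response differs by arm.

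**Much is already covered.** Search-term thrombotic and ischaemic cerebrovascular events receive EAIRs, deaths are tabulated (SAP 8.1.6), exposure is summarised (SAP 4.2.1), and adjudication results are listed. This stands in part. The gap is the adjudicated categories and the MACE composite. A reader could divide adjudicated counts by the PYE published for the search-term events, but only approximately, since PYE under 8.1.5.3 stops at the event and is specific to each outcome. The intervals would also have to be built by hand.

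**The size is assumed, has no sign, and is small.** All true. The ranges span 1, and a gap of 0.3–0.4 percentage points is less than one subject in either column at 125 per arm. This limits the importance. It does not make the percentage the better summary, and with so few events an exact interval tells the reader more than a bare percentage.

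**Conclusion.** The concern holds, with minor importance. Adjudicated MACE, ASTE and VTE get n (%) only, in columns whose exposure per subject can differ, while the SAP's own exposure-adjusted method is applied to the less specific search-term events.

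The exposure ratio was 1.04–1.22 on protocol durations alone and roughly 0.8 to 2.3 once assumed extension patterns are added, so its direction cannot be stated in advance. These figures rest on assumed response, entry, continuation and retention; the event-rate illustrations also assume 1 per 100 PY. For MACE the gap is the adjudicated composite, since its stroke component is partly covered by search terms. The analysis period is not a defect: SAP 3.2 sets the as-treated default and SAP 8.1.5.1 the treatment-emergent window. The primary and secondary semen endpoints are unaffected.

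**What to change.** In SAP 8.1.7.1, keep n (%) and add, for each of positively adjudicated treatment-emergent MACE, ASTE and VTE:

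- as-treated, overall study: PYE, EAIR and exact 95% CI by column;
- double-blind phase: the same, plus the filgotinib minus placebo EAIR difference with its MOVER interval.

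Use the formulas in 8.1.5.3 and the column definitions in 8.1.7, and label each display as as-treated or double-blind.

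The cost is one or two sentences in the SAP and reuse of the existing table program for adverse events of interest. No new data are needed. The intervals will be wide because events will be few.
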